6.3.1 Dose modification and dose interruption

For patients who do not tolerate the protocol-specified dosing schedule, dose interruptions are mandated in order to allow the patient to continue the study treatment. Dose interruption for spartalizumab and/or siltuximab includes delaying or withholding the treatment for any reason as well as an interruption of treatment during an infusion.

The following sections addresses the specific instructions for mandatory dose modifications and recommended management for adverse events considered suspected to be related to spartalizumab and/or siltuximab. These modifications/interruptions must be recorded on the Dosage Administration Record CRF.

6.3.2 Dose modification and dose interruption for spartalizumab and siltuximab

General dose modification instructions:

Siltuximab and spartalizumab have class-specific safety profiles based on their mechanism of action but may also cause AEs that overlap. For management of AEs which can be clearly attributed to siltuximab or spartalizumab, independent dose modification for either agent is allowed. For AEs without clear attribution to either study treatment, management of toxicity should include dose modifications of both agents.

Overall AEs are to be graded according to NCI-CTCAE v4.03 (http://ctep.cancer.gov). All dose interruptions and the reason for the dose interruption must be documented in the eCRF.

Overall, patients with AEs suspected to be related to *spartalizumab* including those of potential immune-mediated etiology (irAE) may need to interrupt or permanently discontinue spartalizumab as outlined in Section 6.3.2. In general, study treatment with spartalizumab must be permanently discontinued in case of:

- Any life-threatening adverse reactions (excluding endocrinopathies controlled with hormone replacement therapy)
- Persistent Grade 2 or 3 adverse reactions (excluding endocrinopathies controlled with hormone replacement therapy) that do not recover to <= Grade 1 within 12 weeks after last dose of study treatment
- Inability to reduce the dose of steroids (for the management of irAE) to 10 mg/day or less of prednisone or equivalent (or as indicated in the tables below) within 12 weeks
- Any severe or Grade 3 recurring treatment-related adverse reaction

The 12 weeks' timeframe will begin from the time the irAE reaches a grade that leads to spartalizumab interruption.

Overall, patients with AEs suspected to be related to *siltuximab* include pruritus, increased weight (edema), rash, hyperuricemia, neutropenia, and upper respiratory tract infection. Rare side effects include gastrointestinal perforation. Toxicities may require interruption of therapy,

Protocol/Version No.: 5, Date December 15, 2022

dose reduction or permanent discontinuation from trial as detailed in section 6.3 and Tables 8-8 and 8-9. In general study treatment with siltuximab must be discontinued for:

- Gastrointestinal perforation
- Grade 4 weight gain
- Grade 4 upper respiratory tract infection
- Recurrent or severe grade 3 treatment-related adverse events.
- Life threatening adverse events
- Interruption of therapy for longer than 12 weeks

If either study drug (siltuximab or spartalizumab) is on temporary hold, therapy with the other agent will continue. Cross sectional imaging will be performed every 3rd cycle as per protocol. If there is disease progression, the subject should be removed from the study. The only exception is siltuximab may be continued as a single agent to control immune-related adverse events (irAEs) attributed to spartalizumab, but siltuximab therapy must be stopped after the irAEs can be adequately controlled with corticosteroids therapy.

If either study drug (siltuximab or spartalizumab) is being **permanently** discontinued, the remaining study drug should also be permanently discontinued given that either drug alone is unlikely to have adequate anti-tumor activity to justify its continuation for a prolonged period of time with the following exceptions:

- 1. In subjects who are demonstrating objective benefit from treatment (radiologic CR, PR or SD), a discussion regarding continuing single agent therapy will be conducted with PI and patient. Subject will be informed single agent activity of either agent is unlikely in pancreatic cancer. If the subject is agreeable, single agent therapy may continue until progression. No single agent therapy beyond progression will be offered.
- 2. Siltuximab may be continued as a single agent to control immune-related adverse events (irAEs) attributed to spartalizumab, but siltuximab therapy must be stopped after the irAEs can be adequately controlled with corticosteroids therapy.

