Patients should be instructed to return to the study site as soon as possible (instead of waiting for their next scheduled visit) if they experience symptoms consistent with an irAE. Patients who experience a new or worsening irAE should be contacted and/or evaluated by the study site more frequently.

Based on experience from compounds with similar mechanism of action of spartalizumab and published guidelines (Haanen, 2017), instructions have been developed regarding how to identify, assess severity and manage irAEs that may occur in patients receiving spartalizumab. Dose modification requirements and AE management guidelines for the potential irAEs are provided in the following tables: diarrhea/colitis (Table 8-0), hepatitis (liver laboratory alterations) (Table 8-1), skin (rash) (Table 8-2), nephritis (Table 8-3), pneumonitis (Table 8-4), endocrinopathies (Table 8-5), and other potential immune-related AEs (Table 8-6). Any Grade 4 irAE must result in permanent discontinuation of spartalizumab. In addition, guidance for management of spartalizumab -infusion reaction & cytokine release syndrome is provided in (Table 8-7).

Under the category of OTHERS (Table 8-9) are included several irAE of interest that must be managed specifically and for which no specific guidance are provided in the table below. OTHERS include (but is not restricted to) the following events: Autoimmune neuropathy, demyelinating polyneuropathy, Guillain-Barre, myasthenia Gravis-like syndrome, non-infectious myocarditis, non-infectious pericarditis, pancreatitis, encephalitis, and, rapid onset of Grade 3 fatigue in the absence of disease progression.

Protocol/Version No.: 5, Date December 15, 2022

Patients receiving spartalizumab, may experience other irAEs than those listed in this document, therefore, all AEs of unknown etiology associated with drug exposure should be evaluated to determine if it is possibly immune-related. In cases where the specific irAE is not listed in the tables below, the investigator should follow the dose modification requirements in section 6.3.2 which details the measures to be taken for suspected (could be potentially immune-related or non-immune-related) AEs. Investigators are encouraged to contact the Sponsor as needed to discuss cases that warrant separate discussion outside of the scope of the current instructions.

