The dosing modification requirements are mandatory, however, the AE management guidelines are recommendations and can be modified according to the local practices.

Table 8.0 Mandatory dose modification requirements and recommended clinical management guidelines for potential immune-related diarrhea/colitis

Diarrhea/Colitis (NCI-CTCAE v	1100/	
Grade	Recommended Adverse Event management guidelines	Mandatory Dose Modification requirements
Grade 1 (< 4 bowel actions per day over baseline) mild Grade 2 (4-6 bowel actions per day over baseline) and / or abdominal pain/ blood in stool.	 Diet Hydration Loperamide: initially 4 mg, followed by 2 mg every four hours or after every unformed stool; maximum 16 mg/day. Continue until diarrhea free for 12 hours; Diarrhea > 24h: loperamide 2 mg every two hours; maximum 16 mg/day. Consider adding oral antibiotics. Diarrhea > 48hrs: loperamide 2 mg every two hours; maximum 16 mg/day. Consider other second-line therapies for diarrhea (e.g: (octreotide, oral diphenoxylate) and oral antibiotics If Grade 2 and no improvement in 5 days may require oral steroids If Grade 2 diarrhea persists >1 week consider Gl consultation and endoscopy to 	Continue spartalizumab treatment If diarrhea is Grade 2, despite loperamide at 2 mg every two hours for > 48hrs:

Protocol/Version No.: 5, Date December 15, 2022

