Symptomatic endocrinopathy (e.g., hypophysitis, adrenal insufficiency, hypothyroidism, hyperthyroidism)	 Consider Endocrinology consultation Rule out infection/sepsis and other alternative causes with appropriate cultures and imaging Treat with an initial dose of methylprednisolone 1 to 2 mg/kg intravenously followed by oral prednisone 1 to 2 mg/kg per day. (only for lifethreatening endocrinopathies) Replacement of appropriate hormones may be required as the steroid dose is tapered Hypophysitis with clinically significant adrenal insufficiency and hypotension, dehydration, and electrolyte abnormalities (such as hyponatremia and hyperkalemia) constitutes adrenal crisis Consider hospitalization and intravenous methylprednisolone should be initiated. 	Interrupt spartalizumab until recovery to mild or no symptoms, and controlled with hormone replacement therapy Once recovered or controlled with hormone replacement, restart spartalizumab at the same dose and schedule Hypothyroidism may be managed with replacement therapy without treatment interruption (unless lifethreatening) Permanently discontinue spartalizumab for lifethreatening endocrinopathies (i.e. hyperthyroidism, adrenal insufficiency, hypophysitis) or recurring severe/lifethreatening events not controlled by hormone replacement therapy.
Autoimmune diabetes (Grade 3 or symptomatic hyperglycemia)	Initiated: Initiate anti-glycemic therapy (i.e. insulin) as medically indicated and monitor glucose levels regularly until metabolic control is achieved	Interrupt spartalizumab until recovery to grade 1 or baseline Once recovered, restart spartalizumab treatment at the same dose and schedule
Autoimmune diabetes (Grade 4 hyperglycemia or life- threatening complications)	Same as Grade 3	 Second occurrence: permanently discontinue Permanently discontinue spartalizumab

Management for immune-related:

Protocol/Version No.: 5, Date December 15, 2022

a. For non-life-threatening immune-related endocrinopathy, the administration of corticosteroids can be omitted, and the patient can be treated with physiologic replacement of the deficient hormone (e.g. provide levothyroxine for immune-related hypothyroidism, and omit administration of corticosteroids).

b. Use corticosteroids only used if endocrinopathy is life-threatening or as physiologic replacement for primary or secondary adrenal insufficiency.

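### For a life-threatening endocrinopathy controlled with hormone replacement, Section 6.3.2 exempts the patient from mandatory permanent discontinuation of spartalizumab, Section 6.3.2.1.1 requires it, and Table 8-5 does not settle which applies

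*Combined protocol and SAP*

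**What the plan says.** Three places in the protocol speak to this patient.

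- **Section 6.3.2, general instructions.** The list opens with "In general, study treatment with spartalizumab must be permanently discontinued in case of", and its first item is "Any life-threatening adverse reactions (excluding endocrinopathies controlled with hormone replacement therapy"). The exclusion sits inside the life-threatening item, so it reaches life-threatening events.
- **Section 6.3.2.1.1.** After naming the tables for each type of immune-related event, with endocrinopathies assigned to Table 8-5, the text states: "Any Grade 4 irAE must result in permanent discontinuation of spartalizumab".
- **Table 8-5, symptomatic endocrinopathy row, mandatory column.** It says "Once recovered or controlled with hormone replacement, restart spartalizumab at the same dose and schedule". Further down the same cell it says "Permanently discontinue spartalizumab for lifethreatening endocrinopathies (i.e. hyperthyroidism, adrenal insufficiency, hypophysitis) or recurring severe/lifethreatening events not controlled by hormone replacement therapy".

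On the force of these texts, Section 6.3.2.1.1 says "The dosing modification requirements are mandatory, however, the AE management guidelines are recommendations". On the partner drug, Section 6.3.2 says that when one agent is permanently stopped "the remaining study drug should also be permanently discontinued". It gives two exceptions: single-agent treatment may continue in a patient with complete response, partial response or stable disease, and siltuximab may continue to control an immune-related event.

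**The concern.** An investigator whose patient has had, for example, a life-threatening adrenal insufficiency and is now stable on replacement needs one answer to whether spartalizumab must be stopped permanently. The protocol gives an exemption in one section and an unconditional requirement in the next. The table that should decide the matter can be cited for either course. Endocrine toxicity is an expected class effect: Section 5.4 places it among the typically most frequent immune-mediated events, and Section 9.1.3 lists it as an event of special interest.

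Two things are at stake. The first is patient safety and consistent conduct, since either action could later be called a deviation. The second is the meaning of the summary in Section 12.5.1.1 of adverse events leading to discontinuation of study drug, because identical events could be counted differently.

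**Working it through.** The plan states no figure on this point, so the check is mainly a comparison of texts.

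**The case.** Take a first life-threatening immune-related endocrinopathy, attributed to spartalizumab and since controlled with hormone replacement. Treat life-threatening as Grade 4. Tables 8.0, 8-2, 8-4 and 8-7 label Grade 4 that way, and Section 9.1.1 makes the same match for events without a CTCAE grading. The symptomatic endocrinopathy row of Table 8-5 uses no grades.

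| Text | Permanent discontinuation required? |
|---|---|
| 6.3.2, life-threatening item | No: excluded from the trigger |
| 6.3.2.1.1, Grade 4 sentence | Yes: no exception |
| Table 8-5, reading A (qualifier attaches only to recurring events) | Yes |
| Table 8-5, reading B (qualifier attaches to both limbs) | No: the restart line applies |

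**Reading A** is the plainer grammar. It also fits the same cell's line on hypothyroidism, which allows replacement without interruption unless the event is life-threatening. The table and the Grade 4 sentence then agree, and the exclusion in 6.3.2 is out of line with both.

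**Reading B** makes the table agree with 6.3.2, and the Grade 4 sentence is then out of line with both.

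Under either reading one text differs from the other two. The inconsistency does not depend on how the table is parsed; the parsing only decides which sentence is the odd one out.

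**Size, per patient.** Section 12.1 gives 27 to 42 treated patients (24 in expansion plus 3 to 18 in escalation). Section 12.3 bases the safety evaluation on everyone who received any study drug, apart from its exclusion for taking under 80% of the prescribed dose. If that exclusion removes nobody:

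- 1/42 = 2.4%
- 1/27 = 3.7%

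**Dose-limiting toxicities.** Table 7 counts a Grade 4 immune-related toxicity of any duration. Within the six-week window the event is a dose-limiting toxicity whether or not spartalizumab is later resumed. The escalation decision and the recommended phase 2 dose therefore do not change. The same holds for the expansion stopping rule in Section 12.1, which uses the Table 7 criteria.

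**The case against.** The best counter-argument is that the protocol does signal an order of precedence. Section 6.3.2.1.1 sends immune-related events that are not listed in the tables to Section 6.3.2, which suggests that listed events are governed by the tables. Section 6.3.2 is headed as general instructions and its list begins with "in general" wording. A site that stops spartalizumab under the specific text breaches nothing in 6.3.2. This is a fair reading, but it rests on implication. It also leads to a table cell that is itself ambiguous, and under reading B to a conflict between that table and the Grade 4 sentence. The exclusion in 6.3.2 names endocrinopathies specifically and would have little purpose if it were always overridden.

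A second objection is rarity. Section 4.1.1.2 reports five patients with treatment-related serious events among 160 in the single-agent study, and none of the events named is an endocrinopathy. With 0/160, the one-sided 95% upper bound is 1 − 0.05^(1/160) = 1.9%. If that carried over to the combination, which is an assumption, fewer than one case would be expected (42 × 0.0185 = 0.78). This stands, and it limits the effect on the trial's summaries. It does not remove the need for one clear instruction when a case occurs.

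Some stronger inferences are tempting but not supported:

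- **That sites face two opposite mandates.** Section 6.3.2 exempts the patient from a trigger; it does not order treatment to continue.
- **That Table 8-5 plainly contradicts 6.3.2.** This holds on reading A only.
- **That the patient necessarily loses both drugs.** The single-agent exceptions in 6.3.2 apply; it is the combination that ends.
- **That response duration would be distorted.** Sections 6.7, 6.7.4 and 14.3 continue tumour assessment until progression after discontinuation for other reasons, so an effect on this endpoint is speculative.
- **That one patient shifts the discontinuation rate by 1/24 = 4.2 points.** The safety denominator is all treated patients, not the expansion cohort alone.

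**Conclusion.** The inconsistency is real and limited. For a life-threatening immune-related endocrinopathy controlled with hormone replacement, Section 6.3.2 exempts the patient from mandatory permanent discontinuation of spartalizumab, and Section 6.3.2.1.1 requires it without exception. Table 8-5 does not resolve the difference. Precedence of the tables is implied but never stated.

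The reading chosen decides whether the patient remains on the combination and whether the event enters the discontinuation summary, at about 2.4 to 3.7 percentage points per such patient. That is a per-patient figure, not an expected shift. The primary objective is untouched. The conclusion rests on equating life-threatening with Grade 4 and on the event being attributed to spartalizumab. It should be corrected because it concerns a mandatory safety instruction that cannot be applied consistently as written, not because it threatens the trial's main result. No view is taken here on which rule is clinically right.

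**What to change.** Reconcile the passages:

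1. In Table 8-5, state once whether the hormone-replacement exception covers life-threatening endocrinopathies. Reword the discontinuation sentence so that its qualifier can be read only one way, and make clear which events the restart line covers.
2. Make the life-threatening item in Section 6.3.2 and the Grade 4 sentence in Section 6.3.2.1.1 refer to Table 8-5 for endocrinopathies.
3. Say outright that the tables take precedence over the general list for the events they name, if that is the intention.

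The clinical team chooses the rule. The cost is a few sentences in a protocol amendment, with no change to sample size, assessments or analysis.

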Grade 3, 4	Monitoring blood test more frequently (every 7 days for grade 3, and 3-5 days for grade 4) Consider consulting with a specialist, initiation of corticosteroids or other therapies as medically appropriate and as per institutional guidelines.	1st occurrence: Interrupt spartalizumab and siltuximab until toxicity recovers to Grade ≤2 or baseline. Once recovered restart spartalizumab and siltuximab treatment at the same dose and schedule Grade 4 febrile neutropenia or thrombocytopenia should lead to permanent discontinuation of spartalizumab and siltuximab 2nd occurrence: Interrupt spartalizumab and siltuximab until toxicity recovers to Grade ≤2 or baseline Once recovered restart spartalizumab and siltuximab treatment at the same dose and schedule
		AE resolution to ≤ Grade 2 or baseline must occur within a maximum period of 12 weeks since Grade 3 or 4 event has been identified, otherwise spartalizumab

Grade	Recommended Adverse Event management guidelines	Mandatory Dose Modification requirements
		and siltuximab must be permanently discontinued
		3 rd occurrence:
		Permanently discontinue spartalizumab and siltuximab
Febrile Neutropenia	Apply Institutional guidelines	Follow- neutropenia Grade 4 requirements (above)
Thrombocytopeni	ia (NCI-CTCAE v4.03)	
Grade 1, 2, 3 without clinical significant bleeding	Grade 3: monitoring blood test more frequently (every 7 days)	Continue spartalizumab and siltuximab
Grade 3 with	Monitoring blood test more frequently	1 st occurrence:
clinical significant bleeding OR Grade 4	(every 3-5 days) Consider consulting with a specialist, initiation of corticosteroids or other therapies as medically appropriate and as per institutional guidelines.	 Interrupt spartalizumab and siltuximab until toxicity resolves to Grade ≤2 or baseline. Once recovered restart spartalizumab and siltuximab at the same dose and schedule
		2 nd occurrence:
		 Interrupt spartalizumab and siltuximab until toxicity resolves to Grade ≤2 or baseline Once recovered restart spartalizumab and siltuximab at the same dose and schedule
		AE resolution to ≤ Grade 2 or baseline must occur within a maximum period of 12 weeks since Grade 3 with clinically significant bleeding or Grade 4 event has been identified, otherwise spartalizumab and siltuximab must be permanently discontinued.
		3 rd occurrence:
		permanently discontinue spartalizumab and siltuximab

Protocol/Version No.: 5, Date December 15, 2022

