Table 8-9 Mandatory dose modification requirements and recommended clinical management guidelines for non-hematologic adverse events suspected related to study treatment (excluding alopecia, grade 2 fatigue and irAE)

Grade	Recommended Adverse Event management guidelines	Mandatory Dose Modification requirements					
Grade 1-2 tolerable	Monitor closely	Continue spartalizumab and siltuximab treatment at the					
	 Provide supportive care according to institutional standards 	same dose and schedule					
Grade 2 intolerable or	 Monitor closely 	1 st or 2 nd occurrence:					
Grade 3	 Provide supportive care according to institutional standards 	 Interrupt spartalizumab and siltuximab until toxicity recovers to Grade ≤1 or 					
	 Consider consulting with a specialist, initiation of corticosteroids or other therapies as medically appropriate and as per institutional guidelines. 	 baseline. Once recovered restart spartalizumab and siltuximab at the same dose and schedule 					
		AE resolution to Grade ≤1 or baseline must occur within a maximum period of 12 weeks since intolerable Grade 2 or Grade 3 event has been identified, otherwise spartalizumab and siltuximab must be permanently discontinued.					
		3 rd occurrence: Permanently discontinue spartalizumab and siltuximab					
Grade 4	Monitor closely	1 st occurrence:					
	 Provide supportive care according to institutional standards Consider consulting with a specialist, initiation of corticosteroids or other therapies as medically appropriate and as per institutional guidelines. 	 Interrupt spartalizumab and siltuximab Consider permanently discontinuing spartalizumab. If benefit risk assessment support treatment continuation, restart spartalizumab and siltuximab at the same dose and schedule. 					

Protocol/Version No.: 5, Date December 15, 2022

Non-Hematologic suspected AEs (except Grade 2 alopecia, Grade 2 fatigue, irAE) (NCI-CTCAE v4.03)						
Grade	Recommended Adverse Event management guidelines	Mandatory Dose Modification requirements				
		2 nd occurrence:				
		Permanently discontinue spartalizumab and siltuximab				

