6.3.3 Dose modifications Siltuximab

Table 9. Dose reduction steps for siltuximab

Overall, patients with AEs suspected to be related to siltuximab include pruritus, increased weight (edema), rash, hyperuricemia, and upper respiratory tract infection. Rare side effects include gastrointestinal perforation.

Each patient can receive a maximum of 2 dose reductions of siltuximab prior to permanent discontinuation of siltuximab.

Siltuximab can be held for a maximum of 12 weeks, if no resolution of toxicity to grade 1 or less, then siltuximab will be permanently discontinued.

Dose reduction*											
Starting dose level – 0 Dose level – 1 Dose lev											
Siltuximab	11 mg/kg	9 mg/kg	6 mg/kg **								
*Dose reduction should be based on the worst toxicity demonstrated at the last dose.											
**Dose reduction below 6 mg/Kg is not allowed.											

- 1. Weight gain due to edema **grade 1 or 2** manage symptomatically with diuretics. Patients with **grade 3** hold siltuximab treat symptomatically resume at one dose level lower once grade 1. Patients with **grade 4** hold siltuximab and treat symptomatically. Permanently discontinue siltuximab for first occurrence of grade 4 weight gain.
- 2. Hyperuricemia grade 1 or 2 continue treatment with siltuximab and monitor. Grade 3 start therapy for hyperuricemia (allopurinol) and hold siltuximab until it resolves to grade 1. Resume at a lower dose level. Grade 4 hold siltuximab permanently, treat hyperuricemia (rasburicase).

Protocol/Version No.: 5, Date December 15, 2022

3. Upper respiratory tract infection grade 1 and 2 treat infection and continue siltuximab. Grade 3 or 4 hold siltuximab treat infection. First occurrence of grade 4 upper respiratory tract infection will lead to permanent discontinuation of siltuximab. For Grade 3, resume after infection treated no dose reduction for first occurrence. Dose reduce by one dose level for second occurrence. Hold permanently for third occurrence.

- 4. Pruritus grade 1 and 2 treat symptomatically and continue siltuximab. Grade 3 hold siltuximab, treat symptomatically, resume siltuximab after symptoms resolve.
- 5. Gastrointestinal perforation any grade permanently hold siltuximab.
- 6. Dose modifications of siltuximab for hematologic and non-hematologic toxicities also review 6.3.2.2.

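### For repeat related Grade 3 events that are not irAEs, 6.3.2 stops study drug but Tables 8-8/8-9 and 6.3.3 do not; separately, 6.3.3 orders siltuximab reductions that cannot be given at 6 mg/kg

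*Combined protocol and SAP*

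**What the plan says.** Section 6.3.2 has two lists of reasons for stopping. Each is introduced as a general rule and each is worded as an obligation. One spartalizumab entry is "Any severe or Grade 3 recurring treatment-related adverse reaction"; the siltuximab counterpart is "Recurrent or severe grade 3 treatment-related adverse events". Just before the siltuximab list, the text says that toxicities may need interruption, "dose reduction or permanent discontinuation from trial as detailed in section 6.3 and Tables 8-8 and 8-9". Later, 6.3.2 says that when one drug is stopped for good, "the remaining study drug should also be permanently discontinued given that either drug alone is unlikely" to be active enough by itself. The exceptions are patients with CR, PR or SD, and siltuximab kept on to control irAEs.

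Tables 8-8 and 8-9, in 6.3.2.2, are titled as mandatory. For Grade 3 or 4 neutropenia, Table 8-8 reads "2nd occurrence: Interrupt spartalizumab and siltuximab until toxicity recovers to Grade ≤2 or baseline Once recovered restart spartalizumab and siltuximab treatment", with a permanent stop at the third occurrence. For a first or second Grade 3 non-hematologic event, Table 8-9 reads "Once recovered restart spartalizumab and siltuximab at the same dose and schedule", again stopping at the third. The heading of Table 8-9 excludes irAEs.

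Section 6.3.3 resumes siltuximab at a lower dose after Grade 3 weight gain from edema (item 1) or Grade 3 hyperuricemia (item 2). For Grade 3 upper respiratory infection (item 3) it says "Dose reduce by one dose level for second occurrence. Hold permanently for third occurrence". Table 9 steps from 11 to 9 to 6 mg/kg, and its footnote rules out anything lower. Cohort 1 starts at 6 mg/kg (6.2.2).

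**The concern.** Two mandatory instructions give different answers for the same patient. An investigator facing a second related Grade 3 event can stop both drugs under 6.3.2, or restart both under the tables, and be following the protocol either way. Because stopping one drug normally stops the other, the choice usually decides whether the patient leaves all study treatment.

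The choice can also reach the primary endpoint. Table 7 counts any adverse event that leads to permanent discontinuation of either drug as a DLT, so for some events the management rule decides whether a DLT is recorded.

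At 6 mg/kg the problem is different: 6.3.3 gives an order that Table 9 forbids, and no alternative is written.

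**Working it through.** No plan figure depends on these rules, so the check sets the texts side by side.

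**Second occurrence of a related Grade 3 event that is not an irAE**

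| Event | 6.3.2 lists | Specific rule |
|---|---|---|
| Neutropenia | Stop | Table 8-8: restart both, same dose; stop at third |
| Non-hematologic, general | Stop | Table 8-9: restart both, same dose; stop at third |
| Upper respiratory infection | Stop | 6.3.3 item 3: siltuximab down one level; stop at third |

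**Does the text settle precedence?**
- For the tables: both 6.3.2 lists are introduced as general, and 6.3.1 says that the sections after it hold the specific instructions.
- The pointer to Tables 8-8 and 8-9 stands in the siltuximab paragraph only. The spartalizumab paragraph refers to 6.3.2 itself.
- Against the tables: 6.3.2.2 limits them to related events with no specific management requirement elsewhere in the protocol. A reader could take the 6.3.2 bullets as such a requirement.
- The siltuximab bullet also names a severe form of Grade 3, which is not defined.

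**Which events change the DLT count?** The event must recur within the 6-week window and must not already be a DLT under Table 7.
- Edema weight gain, hyperuricemia and respiratory infection: no change. A related Grade 3 event already counts as other non-hematologic toxicity.
- Neutropenia: Table 7 lists only Grade 4 lasting more than 8 days, and febrile neutropenia. A second Grade 3 neutropenia is a DLT if 6.3.2 stops the drug, and is not if Table 8-8 restarts it.
- Nausea or vomiting: Table 7 requires at least 72 hours despite treatment. A second shorter Grade 3 episode is in the same position.

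**What can one such patient do?** Under 6.2.2, moving from 0/3 to 1/3 adds up to 3 patients, and moving from 1/6 to 2/6 means the MTD is exceeded. The expansion stopping rule in 12.1 also relies on Table 7.

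**How easily would it be seen?** The only scheduled blood count after the first dose and before day 42 is at cycle 2 day 1, about day 22. The next is about day 43 (±3 days). The day 8 and 15 visits list chemistry only (8.1.3). Table 8-8 recommends weekly counts after Grade 3 neutropenia, so a recurrence after a day-22 finding could be detected. Vomiting needs no laboratory visit, and the doses on days 1 and 22 both fall in the window.

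**Reduction steps available under Table 9**
- Start at 11 mg/kg: 11 to 9 to 6, two steps.
- Start at 9 mg/kg: 9 to 6, one step.
- Start at 6 mg/kg: none.

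The allowance of two reductions in 6.3.3 therefore fits only an 11 mg/kg start. All 3 to 6 patients in cohort 1 have no step, nor has anyone already reduced to 6 mg/kg.

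**The case against.** The strongest reply on precedence is that 6.3.2 is a general summary that sends the reader to specific tables, so the ordinary reading is that the tables govern. That is the likelier reading. It is still an inference: the pointer covers one drug only, and the scope sentence in 6.3.2.2 points the other way.

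On the dose floor, the reply is that the patient is held first, no permitted lower dose exists, and 6.3.2 requires discontinuation once an interruption exceeds 12 weeks, so the text does reach an endpoint. It is true that nothing permits an unsafe dose. But a patient whose toxicity resolves early could be held until the limit, stopped at once, or resumed at 6 mg/kg. These are not equivalent: during a temporary hold 6.3.2 continues the other drug, whereas permanent discontinuation normally ends both.

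A further reply is that escalation is decided in one working group with DSMC approval, and that Grade 2 or higher events are reviewed first. This limits inconsistent DLT counting. A reader might infer that the DSMC has no way to classify such a patient, but Table 7 supplies the rule: a permanent discontinuation for an adverse event is a DLT. What is unclear is the earlier step, whether the patient should have been discontinued.

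**Conclusion.** Both parts hold on the current text. The first is an unresolved conflict between mandatory rules for repeat related Grade 3 events that are not irAEs. The second is a definite gap for 3 to 6 cohort 1 patients and an unknown number later reduced to 6 mg/kg. The main consequence is inconsistent patient management.

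Three stronger readings are not supported.
- A reader might infer that dose escalation is materially distorted. The DLT effect is confined mainly to a second Grade 3 neutropenia or short nausea/vomiting in the window. The documents give no rate for these, so no size can be put on it.
- A reader might infer that the floor gap covers the 24 expansion patients from their first dose. That needs 6 mg/kg to become the RP2D, which under 6.2.2 means that both 11 and 9 mg/kg fail.
- A reader might infer that the irAE rules conflict too. Table 8-9 excludes irAEs, and the irAE tables that allow a restart after a first Grade 3 event with an occurrence count (diarrhea/colitis, rash, nephritis, other) stop spartalizumab at the second, in line with 6.3.2.

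**What to change.** 1. In 6.3.2, limit the two recurrence bullets. For related Grade 3 events that are not irAEs, the occurrence count in Table 8-8, Table 8-9 or 6.3.3 governs. State that the 6.3.2 stops for life-threatening events, the Grade 4 stops and the irAE tables are unchanged. The Grade 3 limit matters: Table 8-9 allows a restart after a first Grade 4 event, and an unrestricted precedence sentence could override the life-threatening stop. Define or delete the severe Grade 3 wording.
2. In 6.3.3, add that if a reduction is required at 6 mg/kg, siltuximab is permanently discontinued. Note that a 9 mg/kg start has one reduction step and a 6 mg/kg start has none.
3. Leave the discontinuation criterion in Table 7 as it is, so that every permanent discontinuation for an adverse event still counts as a DLT.

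Item 1 adopts the more permissive rule because the pointer in 6.3.2 favours it. If the sponsor prefers to stop at recurrence, the tables and 6.3.3 item 3 should be changed instead. The cost is a short amendment, with no added patients or procedures.
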